Subjects will be recruited from the clinic population at the Yale Children's Diabetes Program who meet eligibility criteria. Additional subjects may be recruited from local advertising and/or the website *clinicaltrials.gov*. Potential subjects may be emailed information regarding the study, including copies of the consent forms, and if interested will be invited to the research center for formal enrollment.

d. Consent Process

The principal investigators, co-investigators, or study coordinators will introduce the studies to eligible participants and their caretakers during routine medical visits or in the form of a mailing or phone call. Prospective subjects/caretakers will have a face-to-face meeting with the investigator and/or study coordinator to address questions about the study rationale, procedures, risks and benefits. In order to identify and clarify any misconceptions, parents/caretakers will be encouraged to describe the research procedures and their associated risks in their own words, followed by correction of any errors by the investigator or study coordinator. All the subjects in the proposed studies will be minors; parent/guardian permission will be obtained for all subjects; additionally, for subjects age 7 or older, subject assent will also be obtained, as per Yale IRB guidelines. The parents/caretakers of participants will be encouraged to ask questions and will be clearly informed about the time required for these studies and their rights of non-participation and/or withdrawal. Caretakers/parents will be given copies of the signed consents to keep. Since personal health information will be collected as part of this research protocol, parents/caretakers will also be asked for authorization to collect this information in accordance with HIPAA and Yale IRB guidelines.

e. Sample Size

We will enroll a convenience sample of 24-48 subjects (8-16 in each of the three age cohorts), the final number depending on whether additional cohorts needed to be repeated at any given age group. There is no formal sample size calculation for this study.

5. Study Procedures

The study will consist of two visits, separated by no more than two weeks: an enrollment visit and a hotel visit.

a. Enrollment Visit

Subjects and parents/caregivers invited to participate in the study will undergo the consent process as described above, and then have the following study procedures:

1) Medical History

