If stopping criteria are NOT met for an age cohort, then after that cohort is completed we will proceed to next lower age cohort after DSMB review and approval. However, even if stopping criteria are not met, additional cohorts at a given age range may be enrolled at discretion of investigators if adjustments to algorithm tuning parameters are desired based on glycemic results and comparison with subjects' pre-study baseline glycemic profiles.

7. Financial Considerations

a. Subject compensation

Subjects/parents will receive \$50 for the enrollment visit and \$100/day for the hotel visit, for a maximum of \$350 compensation for participation.

b. Meal Stipend

All subject meals during the hotel stay will be covered by the study. Parents will receive \$75 per day stipend for their meals and expenses during the hotel stay. Parking at the hotel will be covered by the study.

8. Adverse Event Reporting and Safety Monitoring

a. Definition

Reportable adverse events in this study include any untoward medical occurrence that meets criteria for a serious adverse event or any medical occurrence (expected or unexpected) in a study participant that is study or device-related.

Hypoglycemic events are recorded as adverse events if the event required assistance of another person due to altered consciousness and required another person to actively administer carbohydrate, glucagon, or other resuscitative actions to prevent harm. This means that the subject was impaired cognitively to the point that he/she was unable to treat his or herself, was unable to verbalize his or her needs, was incoherent, disoriented, and/or combative, or experienced seizure or coma. These episodes may be associated with sufficient neuroglycopenia to induce seizure or coma. If glucose measurements are not available during such an event, neurological recovery attributable to the restoration of glucose to normal is considered sufficient evidence that the event was induced by a low plasma glucose concentration.

Hyperglycemic events are recorded as adverse events if the event involved diabetic ketoacidosis, as defined by the DCCT, and had all of the following:

- Symptoms such as polyuria, polydipsia, nausea, or vomiting;
- Serum ketones or large/moderate urine ketones;

- Either arterial blood pH <7.30 or venous pH <7.24 or serum bicarbonate <15; and
- Treatment provided in a health care facility

b. Recording of adverse events

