investigators. The DSMB will be responsible for oversight of the proposed protocol. The DSMB will monitor the ongoing safety of the studies through periodic reports, at least twice a year, provided by the clinical center, and any adverse event reports as described above requiring notification will also include the Chair of the DSMB. The DSMB will meet with Drs. [name] and [name] every six months, either in person or by conference call, to review study progress and adverse events. In addition, the DSMB will meet with study investigators before the initiation of successively younger subject cohorts, for their input on safety, before any subjects are enrolled, in order to approve the monitoring plans for each study phase at their start.

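### A same-age repeat cohort on retuned controller settings can open without prior DSMB review, although a younger age band cannot

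*Combined protocol and SAP*

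**What the plan says.** Section 6.d (Continuation) gives two routes once an age cohort is complete.

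- **Younger band.** If stopping criteria were not met, "we will proceed to next lower age cohort after DSMB review and approval".
- **Same band again.** The next sentence says that "even if stopping criteria are not met, additional cohorts at a given age range may be enrolled at discretion of investigators", and the condition is "if adjustments to algorithm tuning parameters are desired based on glycemic results and comparison with subjects' pre-study baseline glycemic profiles". No DSMB step is attached.

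Section 8.e (Data Safety Monitoring Board) follows the same pattern: "the DSMB will meet with study investigators before the initiation of successively younger subject cohorts". That sentence ends by referring to approval of monitoring plans for each study phase, a term the protocol does not define.

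Section 4.e (Sample Size) shows that repeats are part of the plan. It sets 24-48 children, 8-16 per age band, "the final number depending on whether additional cohorts needed to be repeated at any given age group". It adds: "There is no formal sample size calculation for this study".

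**The concern.** A repeat cohort is opened in order to try different tuning, so its children are the first in the study to receive insulin from the changed settings. The background section presents the tunable response to hyperglycemia as a core feature of the controller. It also says that young children's sensitivity to insulin makes small dosing errors hazardous. The plan already accepts that independent approval is needed when the population changes. It asks for none when the controller's tuning changes, and within the protocol's own rules the investigators who choose the new tuning also decide that the next group may receive it.

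What is at stake is prior independent review of a changed insulin-delivery algorithm in children. How results from differently tuned cohorts are later combined is a separate matter.

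**Working it through.** **1. Does any DSMB contact have to come before a retuned repeat cohort?**

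| DSMB contact | Where | Trigger | Tied to a retuned same-age cohort? |
|---|---|---|---|
| Review and approval | 6.d | Move to the next lower band | No |
| Pre-cohort meeting | 8.e | Successively younger cohorts | No |
| Enrolment hold until review | 5.b.7, 6.c | Seizure, ketoacidosis or loss of consciousness in any child | No |
| Meetings every six months; reports at least twice a year | 8.e | Calendar | No; may fall before a repeat by chance |
| Notice within 5 days | 8.d | Device event that is both serious and unexpected | No |
| General oversight of the protocol | 8.e | None stated | No specific step |

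None of the six is triggered by a tuning change or by the opening of a repeat cohort.

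**2. Would a calendar meeting catch it anyway?** Section 5 puts the two visits no more than two weeks apart, and the hotel stay lasts up to 60 hours (60 / 24 = 2.5 days). A child's participation is therefore short compared with six months, and a repeat cohort could fall between two meetings. The recruitment pace and the number of children per hotel session are not given, so this is possible but cannot be shown to be likely.

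**3. Does a later gate make up for it?** In the two older bands, the DSMB reviews before the next younger band opens, which is after the repeat cohort has been treated. In the under-8 band there is no next band, so no cohort-linked review follows.

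**4. How many children?** The plan's range reproduces: 3 bands x 8 = 24 and 3 x 16 = 48. The size of a first cohort is not stated separately from the 8-16 per band. *Assumption:* first cohorts of 8, and one repeat of 8 in each of k repeated bands. Then

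share in repeat cohorts = 8k / (24 + 8k)

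| Bands repeated (k) | Children in repeats | Total | Share | Closed-loop hours at the 60 h maximum |
|---|---|---|---|---|
| 0 | 0 | 24 | 0% | 0 |
| 1 | 8 | 32 | 25% | 8 x 60 = 480 |
| 2 | 16 | 40 | 40% | 16 x 60 = 960 |
| 3 | 24 | 48 | 50% | 24 x 60 = 1,440 |

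*Sensitivity to the assumption:* if every band reaches 16 and the first cohort holds b children, the share is (16 - b) / 16. This gives 25% for b = 12, 37.5% for 10, 50% for 8, 62.5% for 6 and 75% for 4.

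**The case against.** The strongest reply is that the DSMB is far from absent. It oversees the protocol, and so has sight of the discretion in 6.d. It meets every six months, is notified of serious and unexpected device events, and must review before enrolment resumes after a severe event. Repeat cohorts stay in an age band already studied, with on-site staff, text alerts, midnight glucose checks and individual stopping criteria. All of this stands. It protects the individual child and provides review after the fact, but it does not put a particular tuning change before the DSMB in advance.

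The undefined term study phase in 8.e could be read to cover repeat cohorts. In its sentence it more naturally belongs to the younger cohorts, so it needs clarifying and does not close the gap.

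Four stronger inferences are tempting, and the documents do not support them.

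- *That DSMB review is tied only to younger bands, or that a retuned controller would get no independent check at all.* Calendar and event reviews exist, and the protocol does not say whether the IRB or FDA would look at a tuning change. What can be said is that no prior DSMB review is required.
- *That half the children will be affected.* That figure needs first cohorts of 8, a retuned repeat in all three bands and full enrolment. It is not an expected share. Nor is it a strict upper limit, as the sensitivity figures show.
- *That retuning is at least as risky as moving to a younger band.* Nothing in the documents compares the two.
- *That 6.d lets investigators answer several individual stops with a retuned repeat and bypass the DSMB.* The discretion clause is framed for cohorts in which stopping criteria were not met, and section 3 defines success in the same way. Whether individual stops mean that the criteria were met for the cohort is not defined. That is a related but separate gap.

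**Conclusion.** The point holds as an omission in the oversight rule. Sections 6.d and 8.e require prior DSMB involvement for a younger band and not for a same-age cohort on changed tuning, and no other provision supplies it. This follows from the text alone and needs no numerical assumption.

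The size does rest on assumptions. With first cohorts of 8 and one repeat of 8 per repeated band, between 8 and 24 children would be involved once at least one band is repeated (25% to 50% of those enrolled), and none if no band is repeated. The consequence is greatest in the under-8 band. The change is worth making because the plan already uses this gate and extending it costs little. The planned enrolment range is unaffected.

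**What to change.** 1. **Amend 6.d and 8.e.** Require DSMB review and approval before any new cohort, younger or same-age, whose tuning parameters differ from those last reviewed. A telephone review would suffice; 8.e already accepts that format for the six-monthly meetings.
2. **Specify the review package:** old and new tuning settings, and from the preceding cohort the individual stops, confirmed BG below 50 mg/dL, BG at or above 300 and 400 mg/dL, and ketone events.
3. **Define study phase in 8.e** so that it expressly includes repeat cohorts.
4. **Separately, reconcile 6.d with the individual stopping criteria in 5.b.7 and 6.c.** State when stopping criteria count as met for an age cohort, and that the DSMB sees those data before a repeat cohort opens.

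The cost is wording in these sections, at most one extra DSMB call per repeat cohort, and a short delay before that cohort opens. None of this prescribes a tuning setting or a clinical rule.

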≥ 400	Any		Notify MD/NP SQ insulin correction, set change Suspend closed-loop May restart if the investigator concludes that the issue is related to a site failure and not due to malfunction of the controller, $BG 80-250\text{mg/dL}$ and ketones $< 0.6\text{ mmol/L}$. Encourage oral fluid intake.	Repeat BG and ketones in 1 hour
Any	>1.0 for $>2\text{h}$ or >3.0 once		STOP system Notify MD/NP SQ insulin correction, set change End closed-loop STOP study for this patient	Repeat BG and ketones in 1 hour

Any	Any	Abdominal pain, vomiting, altered level of consciousness	STOP system Notify MD/NP SQ insulin correction, set change End closed-loop STOP study for this patient Transfer to ER for further Tx	Per clinical scenario
-----	-----	--	---	-----------------------

9) End of Hotel Visit

At the conclusion of the hotel visit (afternoon of 3rd day), subjects will return to their usual pre-study insulin pump and regimen. Study devices will be returned and uploaded for data analysis. Subjects and parents will participate in semi-structured interviews and/or focus groups to give opinions about system usability, confidence in system safety, fear of hypoglycemia, and diabetes-related distress. Study staff will call subjects/parents approximately 24 hours after discharge to review BG control and assess for late adverse events.

10) Surveys and Interviews

Subjects and parents/caregivers will, at the conclusion of the hotel visit, complete several surveys/questionnaires to assess the effect of the closed-loop system on diabetes-related quality of life and distress, fear of hypoglycemia, and satisfaction with diabetes technology (see Table 2). Subjects and caregivers will also participate in focus groups or semi-structured interviews related to human factors issues, and perceived burdens and benefits, of the closed-loop system. Only the interviewer and participant(s) will be present during the interview/focus group.

Table 2. Surveys/questionnaires to assess effect of the closed-loop AP system.

CONSTRUCT:	MEASURE:
CHILD/ADOLESCENT SURVEYS	
Fear of hypoglycemia	Hypoglycemia Fear Survey
Diabetes burnout/burden	Problem Areas in Diabetes
Quality of life–diabetes specific	Pediatric QoL Inventory (PedsQL) – Diabetes Module (8-12)
Quality of life–diabetes specific	Pediatric QoL Inventory (PedsQL) – Diabetes Module (13-18)
Automated Insulin Delivery Device Acceptance	INSPIRE AID Acceptance (Draft) - Child

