Throughout the course of the study, all efforts will be made to remain alert to possible adverse events or untoward findings. The first concern will be the safety of the participant, and appropriate medical intervention will be made. The study investigator will assess the relationship of any adverse event to be related or unrelated by determining if there is reasonable possibility that the adverse event may have been caused by the study device or study procedures.

The intensity of adverse events will be rated on a three-point scale: mild, moderate, or severe. It is emphasized that the term severe is a measure of intensity: thus a severe adverse event is not necessarily serious. For example, itching for several days may be rated as severe, but may not be clinically serious.

Adverse events that continue after the participant's discontinuation or completion of the study will be followed until their medical outcome is determined or until no further change in the condition is expected.

c. Reporting serious or unexpected device-related events

A serious adverse event is any untoward occurrence that:

- Results in death
- Is life-threatening; (a non life-threatening event which, had it been more severe, might have become life-threatening, is not necessarily considered a serious adverse event)
- Requires inpatient hospitalization or prolongation of existing hospitalization
- Results in significant disability/incapacity
- Is a congenital anomaly/birth defect

d. Unanticipated adverse device event

An unanticipated adverse device event is defined as an adverse event caused by, or associated with, a device, if that effect or problem was not previously identified in nature, severity, or degree of incidence.

Serious or unexpected adverse events must be reported to the PI immediately. The PI will notify the Yale IRB, DMSB, FDA, and device manufacturer of any adverse device event that is both serious and unexpected. Notification will be made within 5 days after the PI becomes aware of the event, as per Yale IRB requirements.

e. Data Safety Monitoring Board (DSMB)

Drs. [name] and [name] will convene a Data Safety Monitoring Board, (DSMB), comprised of independent clinicians experienced in the management of young children with type 1 diabetes, to review study protocols and safety reports with study

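### Outside the severe-hypoglycemia and DKA definitions, a non-admitted event judged unrelated need not be a reportable adverse event, even when Table 1 required glucagon, removal or ER transfer

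*Combined protocol and SAP*

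**What the plan says.** Section 8.a opens with two classes. The first is set by seriousness: "Reportable adverse events in this study include any untoward medical occurrence that meets criteria for a serious adverse event". The second is set by relatedness: "any medical occurrence (expected or unexpected) in a study participant that is study or device-related".

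Two event types follow that are recorded with no test of seriousness or relatedness. For hypoglycemia: "Hypoglycemic events are recorded as adverse events if the event required assistance of another person due to altered consciousness", and the event must also have "required another person to actively administer carbohydrate, glucagon, or other resuscitative actions to prevent harm". For hyperglycemia, the event must be DKA with all four of symptoms, ketones, acidosis and treatment in a health care facility.

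The only care-based item in the serious list of section 8.c is "Requires inpatient hospitalization or prolongation of existing hospitalization". The list has no item for ER treatment, for intervention needed to prevent a worse outcome, or for a medically important event.

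Table 1 (section 5.b.8) ends the study for a child in three rows: seizure, loss of consciousness or inability to take oral treatment (with glucagon); ketones above 1.0 mmol/L for more than 2 hours or above 3.0 mmol/L once; and abdominal pain, vomiting or altered consciousness at any glucose and ketone level. The last of these rows adds "Transfer to ER for further Tx". Nothing in the documents says that a Table 1 stop or transfer is itself an adverse event.

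**The concern.** Table 1 and section 8 were not written to the same list of events. Table 1 acts on symptoms, ketones and the need for rescue. Section 8 asks whether the event is serious, whether it is related, or whether it fits one of two narrow definitions. A child can therefore be taken off the study for safety without the event having a required place in the adverse event report.

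This matters because safety is the primary endpoint, there is no control arm, each age group has only 8 to 16 children, and the results decide whether younger children are enrolled. Relatedness is judged by an investigator who knows that the child was on closed loop. If that judgement decides whether an event is reported, instead of being recorded alongside it, the DSMB cannot review the judgement for the events it removes.

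**Working it through.** No arithmetic decides this point. The check takes each kind of Table 1 removal, rescue or transfer through sections 8.a, 8.c and 6.c. In rows 1 to 3 the child is not admitted, no other 8.c criterion is met, and the investigator judges the event unrelated.

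| Event | Serious (8.c) | Related (8.a) | Hypoglycemia or DKA definition (8.a) | DSMB trigger (6.c) | Must be reported or recorded as an adverse event? |
|---|---|---|---|---|---|
| 1. Vomiting or abdominal pain, removed, ER transfer, no qualifying DKA | No | No | Neither | No | No |
| 2. Ketones above 3.0 mmol/L, or above 1.0 for over 2 hours, no acidosis; removed | No | No | Neither | No; stops the child only | No |
| 3. Glucagon for inability to take oral treatment, consciousness intact; removed | No | No | Neither; altered consciousness is required | No | No |
| 4. Hypoglycemic seizure or loss of consciousness, rescued on site | Only if classed as life-threatening | Not needed | Hypoglycemia | Yes | Yes |
| 5. DKA with all four elements, treated in the ER, not admitted | Not needed | Not needed | DKA | Yes | Yes |

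Rows 1 to 3 are the gap; rows 4 and 5 are not. Row 2 is partly covered elsewhere: item 4 of the primary endpoint (6.a) counts those ketone levels unless they are put down to an infusion site failure.

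**Whether rows 1 to 3 reach the DSMB.** Section 6.c pauses enrolment for DSMB review only after seizure, loss of consciousness or ketoacidosis. Section 8.d sends to the IRB, DSMB, FDA and manufacturer only device events that are both serious and unexpected, and these events are not serious. Sections 6.d and 8.e require DSMB review before each younger cohort, but do not say that removals, glucagon use or ER transfers must be listed for it.

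**Consistency of sections 6 and 8.** Three mismatches appear.
- Item 5 of 6.a turns on significant adverse events, a term that section 8 does not define.
- The seizure in row 4 fails item 5 and halts enrolment, yet if the child is not admitted it is serious under 8.c only if classed as life-threatening. There the text adds that "a non life-threatening event which, had it been more severe, might have become life-threatening, is not necessarily considered a serious adverse event".
- Section 6.c defines ketoacidosis by CO2 below 15 mEq/L or pH below 7.3, with no sample type. Section 8.a uses arterial pH below 7.30, venous pH below 7.24 or bicarbonate below 15, plus the other three elements. A child with a venous pH from 7.24 to below 7.30 and bicarbonate of 15 or more, with no arterial sample, meets 6.c (if its pH limit covers venous samples) but not the 8.a definition.

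**Size.** One child is 1/8 = 12.5% of the smallest cohort and 1/16 = 6.25% of the largest. These are shares of a cohort, not probabilities.

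**The case against.** A reader might infer that only serious or related events are reportable. The documents do not support that. Section 8.a says that reportable events *include* those classes, and then records altered-consciousness hypoglycemia, with on-site glucagon written into the definition, and facility-treated DKA on their own terms. Nor does a hypoglycemic seizure reversed at the hotel disappear: it is recorded, it halts enrolment until the DSMB reviews it, and it fails the primary endpoint. What is open there is its label as serious or not.

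It can also be said that section 8.b captures unrelated events first: "The study investigator will assess the relationship of any adverse event to be related or unrelated". An unrelated category implies that some such events are recorded. Section 8.d also sends *unexpected* adverse events to the PI with no test of relatedness. The relatedness threshold, a reasonable possibility, is low. The DSMB sees adverse events every six months and meets before each younger cohort, and a child missing from a group of 8 would be hard to overlook. Leaving out a truly unrelated illness does not distort the device's safety record.

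Much of this stands, and it narrows the point. It does not close it. Sections 8.b and 8.d both start from something already identified as an adverse event, and the 8.d route stops at the PI. That the DSMB would probably notice is not a requirement that it be told. Whether an illness was truly unrelated is the judgement that the DSMB should be able to see.

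**Conclusion.** The point holds in a limited form. A Table 1 removal, glucagon use or ER transfer need not be a reportable adverse event when five conditions coincide: no admission, no other 8.c criterion, no altered-consciousness hypoglycemia, no DKA meeting all four elements, and a judgement of unrelated. Such an event is also not certain to reach the DSMB that approves the next younger cohort.

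The documents give no rate for this combination, so 12.5% shows only what one child weighs in a cohort of 8. A reader might go further and conclude that the safety record is biased, or that every ER transfer should be an SAE. The first is a possibility that the documents do not quantify. The second is a debatable reclassification: Table 1 sends a child to the ER for abdominal pain at any glucose level, and reporting that event does not require calling it serious.

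This is an inexpensive improvement to the safety record, not a flaw that invalidates the design. It assumes that section 8 is the whole reporting rule and that no separate manual requires these events to be listed.

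**What to change.** In section 8.a, state that every adverse event from the start of closed loop to the 24-hour follow-up call is recorded whatever its relatedness, and that this includes every Table 1 stop, glucagon use or ER transfer. Keep relatedness as a recorded attribute. State in section 8.e that these events are listed, with the relatedness judgement, in the report that the DSMB reviews before each younger cohort.

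Reconcile 8.a and 8.c with 6.a item 5 and 6.c, so that any event that halts enrolment or fails the primary endpoint is identified in the adverse event report, and define what counts as significant in item 5. Reconcile the differing acidosis definitions in 6.c and 8.a; which limit applies is a clinical matter for the investigators. Do not make every ER transfer an SAE by definition.

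The cost is a few sentences in section 8, the reconciliation with section 6, and a few more adverse event forms per child over about 60 hours plus one call. No dose or treatment rule in Table 1 needs to change.
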